7 STUDY INTERVENTION

7.1 Study Intervention Administration

7.1.1 Study Intervention Description

The metaMe Health digital GDH product for IBS is named Regulora. Regulora is an IBS-specific treatment platform delivered via a smartphone, tablet, or personal computer. The delivery platform for EASITx is a mobile app available in the Apple and Android app stores under the name of EAGLEFISH. The GDH treatment module was adapted from a standardized scripted therapist-administered GDH protocol referred to as the North Carolina Protocol (10,27). The North Carolina protocol has been licensed by metaMe Health from the inventor ([name]) for exclusive use through any electronic means.

The North Carolina protocol differs from standard hypnotherapy through the use of intensive relaxation methodology, IBS-specific use of metaphor, symptom imagery, and direct and indirect suggestion (27). The North Carolina protocol consists of 7 unique treatment sessions each lasting ~30 minutes provided every-other week over 12 weeks. The first half of the 30-minute treatment session is spent producing deep physical and autonomic relaxation, along with a mental state of narrowed focus of attention and heightened receptivity to suggestions, commonly referred to as the trance state. This is followed by the use of metaphorical storytelling, and a combination of direct and indirect suggestions targeted at somatic control and perception mechanisms that influence IBS symptoms. The treatment sessions are iterative and progressively build relaxation skills, which are required to maximally incorporate the disease-specific aspects of treatment. Subjects become familiar with the use of hypnotherapy tools such as counting and the use of imagery focused on the senses, i.e., touch, smell, sight and hearing (see [Appendix B](#) for scripts of the 7 sessions). As treatment sessions progress, direct suggestion and metaphor are used to overcome the exaggerated response to pain signals imparted by the anticipatory response to IBS symptoms.

The comparator control group will listen to digital video/audio recordings of 7 guided muscle relaxation (MR) sessions of approximately equivalent length to the GDH sessions (see [Appendix D](#) for session scripts), as well as a daily practice session approximately equivalent in length to the GDH practice sessions (see [Appendix E](#) for script) (9). Guided MR was chosen as the comparator control treatment after consultation with the FDA because of (a) the ease with which it can be adapted to a digital format and support the creation of a comparator treatment and (b) credibility as a treatment for IBS albeit with limited demonstrated efficacy (9).

The GDH and MR treatment modules consist of seven ~30-minute digital video and audio recordings of a female therapist. The video component of the treatment sessions occurs at the beginning of the treatment session and is used to simulate the face-to-face interaction of the therapist encounter. The video component is short and typically lasts less than 5 minutes before the screen goes black and subjects are taken through the audio component of treatment. The digital production of the GDH and MR scripts was a verbatim reading. In the case of the GDH scripts the therapist reader provided hypnotherapy-appropriate speech patterns (inflection, pause, and tone). Once therapy is initiated, subjects receive all 7 treatment sessions, every other week for a total treatment period of 12 weeks. During the 13 days between treatment sessions, a short audio session referred to as a “practice session” is made available to subjects. There is a single practice session script for each of the two treatment arms lasting 15 minutes. Subjects receive text message and email reminders with a recommendation to complete a minimum of three practice sessions during the 13 days between treatments. Practice sessions are recommended but not required (see [Appendix C](#) and [Appendix E: Daily Practice Sessions](#)).

The metaMe treatment platform also tracks subject use and progress with treatment modules. For example, the exact time that a subject starts and stops a treatment or practice module is captured by the treatment platform. The software also tracks treatment sessions and only allows subjects to access treatments in sequence. The metaMe treatment platform on the EAGLEFISH app contains these major functional elements:

1. Treatment videos/audios
2. A secure cloud-based data repository.
3. A simple user interface (UI) with an arrow play button that starts the treatment session. (see [Figure 3](#))

In addition to the EAGLEFISH app, subjects enrolled in the EASITx study will be required to enter study data in a second platform. The Curebase platform is for data collection and administers the daily ePRO and provides access to periodic surveys. Subjects will be introduced to the Curebase platform at the baseline screening clinic visit by the research study staff. Study staff will explain the use of the app and the process by which subjects will enter data in the ePRO.

After completion of the 4-week run-in period (Phase 1), subjects will be informed of eligibility, and eligible subjects will be scheduled for a day 0 phone call (scheduled as soon as possible but no more than 14 days from completion of the run-in period). On the day 0 phone call, after a subject is randomized, the Curebase staff will confirm the subject's preferred day of the week, time of day and start date for treatment. Curebase staff will enter the treatment schedule and randomization code (blinded treatment allocation) into a secure metaMe portal that automatically triggers the assigned treatment and the subject-specific treatment reminder and scheduling system. Curebase staff will assist subjects in accessing the metaMe digital platform by guiding them through the process of creating a metaMe login username and password and reviewing the process for accessing the treatment app. Subjects will be guided through the login process and directed to the navigation menu. The navigation menu contains the following items:

1. The home button
2. Account information
3. Treatment schedule
4. Logout
5. Help section. Contains a link to watch or read a transcript to the intro video (see below), FAQ and contact information for technical support and problems with treatment.

[figure not shown]
The treatment process will commence within 7 days of the day 0 call and will be initiated by system-generated text and email reminders of upcoming treatment sessions. Subjects will be sent an email reminder 24 hours and 1 hour before each session, and a text message reminder 5 minutes before each session. Subjects will be able to access the treatment app via a hyperlink in these messages or directly by opening the app on their device. Once in the app, subjects will

initiate treatment by pressing the large arrow start button on the home screen (see User Guide and [Figure 3](#)). The first thing subjects will see is a short 3-minute intro video that explains the following details of treatment:

1. Treatment session length
2. The treatment reminder system, which uses emails and text messages to alert subjects of upcoming treatment sessions and to remind subjects to complete treatment.
3. The process for rescheduling and managing missed treatment sessions (subjects have 3 additional days to complete the treatment before they are considered a missed treatment)
4. Rules on interrupted treatment sessions (subjects must start over from the beginning and have 3 opportunities to finish the treatment before they are considered a missed treatment)
5. The recommended minimum number of practice sessions is 3 over the 13 days between treatments.

There are two intro videos customized to each of the two treatments. They differ in the treatment-specific instructions; in the case of the GDH treatment, the video has specific instructions on how to manage re-alerting after hypnotherapy (see [Appendix F](#)). In the case of the MR treatment, subjects are given guidance on how to manage muscle-specific complaints (see [Appendix G](#)) After the completion of the treatment session, subjects will be instructed to click a button indicating they have completed the session. This button appears upon completion of 100% of the length of the treatment session. A session is also considered completed if greater than 95% of the video is played and no button is pressed by midnight of that day local time. Subjects who miss their scheduled treatment will have 3 additional days in which to complete the treatment. They will receive daily text and email reminders to complete treatment. If after 3 days the subject has not completed the treatment session they will be locked out of that treatment and it will be scored as a missed treatment session. Similarly, subjects will receive a one-time reminder about Practice sessions on the 5th, 8th, and 11th day after each treatment. Subjects will be allowed to access one practice session per day for as many non-treatment days as they like but they will only receive 3 reminders at the indicated days.

The subject experience with the EAGLEFISH app is illustrated in the User Guide and briefly in [Figure 3](#).

Figure 3 metaMe Treatment Visual Narrative**EAGLEFISH User Interface (UI)**

When subjects open the EAGLEFISH app, the main screen appears. The large arrow button, when clicked, is used to access treatment and practice sessions. The first time the button is pressed, the patient will view the introduction video, which is required viewing before the first treatment session and optional thereafter. The app is programmed so that the appropriate content (a treatment or practice session) is displayed each day. Subjects are prevented from re-taking treatment sessions, and subjects cannot access practice sessions on days they have a treatment available (the assigned treatment day plus 3 days in the case that subjects miss treatment on their assigned treatment day). Subjects will be required to complete the treatment/practice session in a single sitting. If the subject is interrupted during treatment, the subject may press the “begin again” button, which starts the session over from the beginning. In this case, subjects will be required to re-start the treatment/practice session from the beginning. Subjects will have 3 days after the initial treatment day to complete treatment sessions. After the treatment/practice session video has played to 100% of its length, subjects may indicate that they have completed the session by clicking on the “Complete Session” button. A session is also considered completed if greater than 95% of the video is played and no button is pressed by midnight of that day local time.

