	
assessment periods starting at 5 months post-treatment (weeks 35 through 38) and 11 months post-treatment (weeks 61 through 64).
 
Participation begins with the completion of an online prescreening eligibility survey via Curebase, a clinical research software platform. Subjects who pass prescreening will be consented online and scheduled for a baseline visit with a study physician. At this visit, their IBS diagnosis will be confirmed, inclusion and exclusion criteria will be applied, and subject-facing surveys administered. Subjects will be trained on the use of the electronic patient reported outcomes tool (ePRO) and daily collection of IBS pain and stool symptoms.
 
The Phase 1 period will begin the day after the baseline visit. The Phase 1 4-week run-in period is a baseline symptom assessment period during which time subjects will enter their IBS symptoms daily and record them digitally via the Curebase ePRO on their mobile phone, tablet, or personal computer. This run-in period will provide baseline symptom data for comparison to post-treatment data collected in Phases 3 and 4. The Phase 1 run-in symptom data is also used to determine whether subjects are committed to participation by assessing their ability to consistently and accurately input data into the ePRO, and also establishes that subjects have the minimally required level of IBS symptom severity.
 
Once the run-in is completed, ineligible subjects will be informed, and eligible subjects will receive an “Onboarding Call” from a member of the Curebase study staff. The Onboarding Call will occur as soon as possible after the Phase 1 run-in period (at least 1 day but not more than 14 days). This call will be used to inform subjects of eligibility, confirm participation, create a user account, confirm access to the platform, and provide training on the use of the metaMe treatment platform. During the Onboarding call, subjects will select a treatment day and time that is maintained throughout treatment (Phase 2). Phase 2 will start on the next occurrence of the chosen weekday. Subjects will be randomized 1:1 into the 2 treatment groups by a firewalled Curebase staff member who will enter the treatment group assignment on the metaMe platform. A software switch will directly initiate the assigned treatment allocation.
 
The study is double-blinded, which in the context of EASITx means that subjects will not be aware of which treatment (GDH or the comparator) is

--	---

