9.3 Populations for Analyses

Enrolled Population: The enrolled population will include all subjects who sign informed consent and meet the inclusion/exclusion criteria. This population will be used for evaluation of demographics and baseline characteristics.

Intent-to-Treat (ITT) Population: The ITT population will include all subjects who are randomized to treatment. Subjects that are replaced due to failed inclusion/exclusion criteria or technical issues in the Curebase software will be excluded. This population will be used for the evaluation of efficacy and all safety analyses.

Per Protocol (PP) Population: The PP population will consist of all subjects in the ITT population with no major protocol deviations that may affect efficacy. This population will be used as a supportive analysis of the primary endpoint.

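### The protocol gives conflicting orders of steps for the day 0 call; if randomization comes first, a subject who cannot get into the treatment app is already in ITT

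*Combined protocol and SAP*

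**What the plan says.** **Section 7.1.1 (Study Intervention Description)** is the only place with an explicit time marker: "On the day 0 phone call, after a subject is randomized, the Curebase staff will confirm" the weekday that the subject prefers, together with the time of day and the start date. The next sentence reads: "Curebase staff will enter the treatment schedule and randomization code (blinded treatment allocation) into a secure metaMe portal that automatically triggers the assigned treatment". Then comes the login step: "Curebase staff will assist subjects in accessing the metaMe digital platform by guiding them through the process of creating a metaMe login username and password".

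**Section 2.1 (Synopsis, Study Design)** says the Onboarding Call serves to inform subjects of eligibility and to "confirm participation, create a user account, confirm access to the platform, and provide training on the use of the metaMe treatment platform". The choice of treatment day and time follows, and only then the sentence on 1:1 randomization.

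**Section 5.1** also mentions account creation before randomization. **Section 2.3** fixes only the day of randomization, and **Section 7.2.2** only that it happens during the call.

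**Section 9.3**: "The ITT population will include all subjects who are randomized to treatment". The one exception is subjects replaced for failed entry criteria or for technical faults in the Curebase software. **Section 8.2** allows replacement for those reasons and no others. The treatment app (EAGLEFISH, on the metaMe platform) is not Curebase software.

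**The concern.** Confirming participation, creating an account, logging in and agreeing a weekday are the same in both arms, and nothing in the documents makes any of them depend on the allocation. A subject lost at one of these steps before allocation is a screen failure and has no effect on the comparison. The same subject lost one step later is a randomized, untreated member of ITT.

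The usual loss allowance may not absorb such a subject. The diary runs on Curebase, and by the day of the call the subject has entered pain scores on at least 70% of run-in days. The payment condition in Section 6.5 is tied to pain surveys, not to treatment sessions. An untreated subject can therefore plausibly supply a complete Phase 3 diary and be analysed as a completer. At stake is some avoidable dilution of the primary responder difference, and an unsettled procedure at the moment of allocation in a pivotal trial.

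**Working it through.** **1. Order of steps**

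| Step | Section 7.1.1 | Synopsis | Section 5.1 |
|---|---|---|---|
| Participation confirmed | not placed | before | not placed |
| Account created | described later, no time marker | before | before |
| App access confirmed | described later, no time marker | before | not placed |
| Weekday and time | confirmed after | selected before | not placed |
| Start date | after | follows from the chosen weekday | not placed |

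Before and after refer to randomization. In the synopsis and Section 5.1 this is the order of sentences, not a stated sequence.

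**2. The plan's own power figure**

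Inputs from Sections 9.1 and 9.2: 150 completers per arm, comparator 26%, difference 18 points (so GDH 44%), two-sided 5%.

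Power = Φ{[d − 1.96·√(2·p̄(1−p̄)/n)] / √([p₁(1−p₁)+p₂(1−p₂)]/n)}

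With p̄ = 0.35: [0.18 − 1.96 × 0.05508] / 0.05409 = 1.332, so power = 90.9%. The stated figure of at least 90% is reproduced.

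The loss allowance is consistent too: 300/0.80 = 375, and 380 × 0.80 = 304.

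**3. Dilution among completers**

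Let f be the share of analysed subjects in each arm who failed on the call but kept the diary. The documents give no value for f. Assume that they respond at the comparator's 26%. Then the GDH rate is 0.44(1−f) + 0.26f, and the difference is 18(1−f) points, a loss of 0.18 point per 1% of subjects.

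| f | Subjects among 300 | Difference (points) | Power, 150 per arm |
|---|---|---|---|
| 0 | 0 | 18.0 | 90.9% |
| 1% | 3 | 17.8 | 90.3% |
| 2% | 6 | 17.6 | 89.8% |
| 5% | 15 | 17.1 | 88.0% |

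If such subjects in both arms instead respond at 17% (the lower control rate cited in Section 9.2), or all count as non-responders, power at 5% is 88.2% or 88.6%. The response assumption matters little.

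**4. If all 380 contribute**

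Section 9.4.1 provides for multiple imputation. With 190 per arm at full information, which is the favourable limit, power is 96.0% at f = 0, 94.2% at 5% and 91.8% at 10%. Section 9.4.2 also requires an observed difference of at least 10 points. At 190 per arm and f = 10%, the chance of meeting that condition is 90.2%, still above 90%.

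**5. Subjects who also stop the diary**

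They are not among the completers. They fall within the planned loss from 380 to 300 and the missing-data handling, so they must not be counted a second time in step 3.

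**The case against.** The strongest reply is that this is only a matter of wording. In Section 7.1.1 the phrase about randomization governs one sentence, on day, time and start date. The login sentence comes two sentences later with no time marker, and confirming a day fits with the subject having chosen it earlier in the call, as the synopsis says. Safeguards also exist: a technology prescreen, a device criterion, a 28-day run-in with a diary rule, and staff who guide the login live. Few subjects are likely to pass all of these and then fail on the call.

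Much of this stands. A reader might infer that the plan definitely randomizes before access is secured. The documents do not support that; they conflict. A reader might also extend the table to f = 10%, where power with 150 per arm is 84.5%. That would require one completer in ten to have failed on the call itself. Treatment starts up to 7 days later, so part of any overall non-starter rate consists of subjects who log in and then never begin, and reordering the call cannot catch them. Nor is there bias in favour of the product: keeping access failures in ITT is conservative and legitimate.

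What does not stand is that the safeguards settle the matter. The run-in tests the Curebase diary, and the device criterion tests ownership. The documents describe no contact with the treatment app before this call. They also give no reason for drawing the allocation first. The schedule and code are entered together, but that does not prevent the schedule from being agreed beforehand.

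**Conclusion.** The point holds as an inconsistency with a modest statistical consequence. The order of steps around allocation differs between Section 7.1.1 on one side and the synopsis and Section 5.1 on the other. Under Section 7.1.1, subjects who fail on the call stay in ITT without replacement.

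The size is conditional. If only 300 completers are analysed, each 1% of them who failed on the call costs roughly 0.6 of a percentage point of power, and the 90% target is missed somewhere between 1% and 2%. If all 380 contribute, the target is kept even at 10%. These figures rest on an assumed rate, on such subjects responding like the comparator, and on their keeping the diary. The change is worth making because it is cheap and cannot bias the comparison, not because the trial's power is in doubt.

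**What to change.** State one order in the synopsis and in Sections 2.3, 5.1 and 7.1.1, all within the same call:

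1. Eligibility and participation confirmed.
2. Account created and login to the treatment app confirmed.
3. Weekday, time and start date agreed.
4. Allocation drawn and entered together with the schedule, as the last step.

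Subjects who fail at steps 1 to 3 are screen failures, which fits the definition in Section 6.4. None of the reasons listed there names failure of app access, so one should be added. Keep ITT as all randomized subjects; removing non-starters after randomization is not a substitute. Report subjects who never start treatment by arm, since this order reduces them but does not remove them.

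Confirmed login is enough. Playing content beforehand is not needed, and the first video shown differs by arm. The sponsor should confirm that login works before the code is entered; the documents do not say otherwise.

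The cost is protocol and call-script wording and a few more screen failures, with no new visit, staff or change to the day of randomization.

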7.2 Measures to Minimize Bias: Blinding and Randomization

7.2.1 Blinding

Blinding of participants to treatment in a psychological or behavioral intervention is generally not possible. By the nature of the intervention, subjects are aware of the type of intervention they are receiving. Instead, in studies involving a psychological or behavioral intervention, blinding the participants to the hypothesis being evaluated in the study is considered the best and most practical strategy for preventing study bias. The EASITx study incorporates this blinding strategy coupled with state-of-the-art IBS and behavioral research methodology.

The comparator-treatment platform will be identical to the GDH treatment platform, except that muscle relaxation (MR) audio recordings equal in treatment duration and frequency of

administration will be substituted for the GDH video/audio recordings. The comparator control group will listen to digital audio recordings of 7 guided muscle relaxation (MR) sessions of approximately equivalent length to the GDH sessions (see Appendix D for session scripts), as well as a daily practice session approximately equivalent in length to the GDH practice sessions (see Appendix E for script) (9). Guided MR was chosen as the comparator control treatment after consultation with the FDA because of (a) the ease with which it can be adapted to a digital format and support the creation of a comparator treatment and (b) credibility as a treatment for IBS albeit with limited demonstrated efficacy (9). The goal of this blinding strategy is to present two treatments that are credible to the study participants, who are themselves unaware of what the other study arm is, whether their assigned treatment (GDH or MR) is the one under study being compared to the other arm, or indeed whether both are active treatments being compared to each other.

The data collection (ePRO) system creates a double blind and eliminates the potential for investigator bias. metaMe staff and investigators will not have knowledge of group assignments, with the following exceptions:

- An independent statistician who will formulate the randomization tables.
- A firewalled Curebase staff member who will enter the treatment group assignment on the metaMe platform.
- A firewalled metaMe staff member (the CTO) who will monitor technical aspects of the study to ensure technical compliance to the protocol and in this capacity may have access to participant randomization assignments.

